9.2.1. Inclusion Criteria

Primary Analysis

This study will include HF patients (defined as having ≥ 1 claim for HF or HF treatment) ≥ 50 years old with clinical diagnosis of ATTRwt-CM or non-amyloid HF ascertained by charts. Patients will be required to have ≥ 12 months of continuous activity in the EHR or claims prior to the Index Date.

Sensitivity analysis (pending feasibility assessment)

1. The earliest HF diagnosis or treatment date as the index date
2. Patients without HF diagnosis or treatment (pending feasibility assessment)
3. High Risk Population:

PFIZER CONFIDENTIAL

CT24-WI-GL02-RF02 4.0 Non-Interventional Study Protocol Template For Secondary Data Collection Study

01-Jun-2022

Page 15 of 25

- Age 65+
- Male gender
- Presence of carpal tunnel syndrome

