9.5. Study size

The sample size formula follows the binomial approach for binary outcomes where:

$$N^{0.5} = (Z_{1-\alpha} + Z_{1-\beta}) (p(1-p))^{0.5} / M$$

For 90% power, the formula results in 78 individuals for sensitivity and 128 individuals for specificity. Using various keyword search, feasibility assessment was performed. In the Optum EHR data, after applying inclusion and exclusion criteria in [Section 9.2.1](#) and [Section 9.2.2](#), there were 422 potential ATTRwt-CM records available; yet, before reviewing the unstructured notes, one is unable to determine the total number of clinically diagnosed ATTRwt-CM patients. Given that ATTRwt-CM is a rare disease for which the ICD-10 code has only been available recently and the use of which clinicians are still not quite familiar with or comfortable using, the team will attempt to maximize the number of

PFIZER CONFIDENTIAL

potential cases by performing note review for all 422 charts. Similar number of control charts will be reviewed to balance the number of cases and controls. Any increase in sample size will result in more precise 95% CIs.

We estimate that the sample sizes will likely provide 90% power to satisfy the non-inferiority hypotheses listed below.

The non-inferiority hypotheses are:

H0: Sensitivity ≤ 0.80

H1: Sensitivity ≥ 0.90

and

H0: Specificity ≤ 0.72

H1: Specificity ≥ 0.82

Sensitivity and Specificity estimates were evaluated based on the validation and performance metrics from the random forest-based ML risk prediction model receiver operating characteristics curve in Huda et al.¹ Sensitivity is defined as the probability that an individual with the disease in the population will screen positive for disease by the algorithm (True Positives). Specificity is defined as the probability that an individual without the disease will be correctly identified as not having the disease by the algorithm (True Negatives).

The distance from H0 to H1 is the non-inferiority margin (NIM), which is 0.10 for both sensitivity and specificity.

For sensitivity, we wish to reject H0 (inferiority to 0.90) in favor of H1 (non-inferiority to 0.90) while for specificity we wish to reject H0 (inferiority to 0.82) in favor of H1 (non-inferiority to 0.82).

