For the validation process using the electronic clinical notes (which will be converted to deidentified structured data for analyses), the Optum Natural Language Programming (NLP) team will determine if clinical notes are available for all qualifying HF patients ≥ 50 years old with a clinical diagnosis of ATTRwt-CM or non-amyloid HF. Optum will perform a series of "enhanced search" queries on the patient notes to determine key term content. Next, the Optum NLP team will use the key terms to extract note snippets into a file for review by the Optum Clinical team. These notes snippets will then be used to validate ATTRwt-CM or non-amyloid HF per Pfizer clinical team specification that were identified in the EHR using the inclusion and exclusion criteria specified in [Section 9.2.1](#) and [Section 9.2.2](#). After clinical review of the notes involving two clinicians from Optum, and categorization of the content for analysis, the resulting table of criteria will be created. The ATTRwt-CM (cases) or non-amyloid HF (controls) will then be classified as validated or not validated, and relevant information entered into a spreadsheet that will serve as the data collection tool. Finally, the Optum clinical review team will provide these results of the case validation to the Pfizer Core Study Team so that the ML algorithm could be run using the structured data to calculate the sensitivity and specificity of the algorithm.

Data will be handled and analyzed using Python software, Version 3.6 or later.

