9.7. Data Analysis

9.7.1. Statistical Methods

The ML model will identify patients with HF as suspected ATTRwt-CM and the remainder patients as not suspected for ATTRwt-CM/non-amyloid HF. The patients with HF will be entered in the ML algorithm along with their diagnosis codes listed in all their records. The model will classify patients based on the presence and absence of cardiomyopathy features and categorized as suspected (at-risk) or not suspected with ATTRwt-CM. The model performance metrics (sensitivity and specificity) will be calculated by cross-tabulating between diagnosis based on ML algorithm and diagnosis based on chart ascertainment.

The analyses for noninferiority of sensitivity and specificity are straightforward. The calculations for these measures are shown below.

PFIZER CONFIDENTIAL

CT24-WI-GL02-RF02 4.0 Non-Interventional Study Protocol Template For Secondary Data Collection Study

01-Jun-2022

Page 19 of 25

Table 1. Sensitivity and Specificity

ML classification	Cohort (Ascertained by Charts)		TP+FP
	ATTRwt-CM	Non-amyloid HF	
+	True Positive (TP)	False Positive (FP)	TP+FP
-	False Negative (FN)	True Negative (TN)	TN+FN
	TP+FN	TN+FP	

Sensitivity = TP / (TP + FN)

Specificity = TN / (TN + FP)

We would then calculate the one-sided 95% confidence interval (CI) for sensitivity, assuming 90% power:

$$95\% \text{ CI} = \text{sensitivity} - 1.645(\text{SE}_{\text{sensitivity}})$$

where $\text{SE}_{\text{sensitivity}} = \text{square root} [\text{sensitivity} - (1-\text{sensitivity})]/n_{\text{sensitivity}}$

The 95% CI for sensitivity must equal or exceed a cut point (CP) value between 0.80 and 0.90 where:

$$\text{CP} = 0.90 - \text{NIM Z1-} \beta / (\text{Z1-}\alpha + \text{Z1-}\beta)$$

When $\alpha = 0.05$ and power = 0.90 we reject inferiority for all values $\geq \text{CP} = 0.8561$.

Similarly, for specificity, we reject inferiority for all values $\geq \text{CP} = 0.7761$.

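### The plan does not say what happens to keyword-identified potential cases that chart review does not confirm, and pooling them unweighted with the controls can change the specificity result

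*Combined protocol and SAP*

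**What the plan says.** Section 9.5 (Study size) plans note review of all 422 potential ATTRwt-CM records and states that the number of clinically diagnosed cases among them is unknown until the notes are read. For the other group it says: "Similar number of control charts will be reviewed to balance the number of cases and controls". It gives neither a method of drawing the controls nor a sampling fraction. The specificity hypotheses are "H0: Specificity ≤ 0.72" and "H1: Specificity ≥ 0.82".

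Section 9.6 (Data Management) describes the result of the review: "The ATTRwt-CM (cases) or non-amyloid HF (controls) will then be classified as validated or not validated". It does not say where a candidate who is not validated goes.

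Three other places work by the diagnosis that the chart supports:
- Section 9.2.1 (Inclusion Criteria) admits HF patients "with clinical diagnosis of ATTRwt-CM or non-amyloid HF ascertained by charts".
- Table 1 in section 9.7.1 has columns for ATTRwt-CM and non-amyloid HF, under a header that begins "Cohort (Ascertained by Charts".
- Section 9.8 (Quality Control) has two clinicians record which of the two diagnoses the notes support.

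Section 9.1 refers to Appendix A for the ascertainment method. In the public document Appendix A is only an icon for an embedded file.

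**The concern.** Some suspects will be rejected on the plan's own reasoning: section 7 says that a diagnosis code often reflects screening for the disease rather than a confirmed diagnosis. The number could be large.

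If the chart label decides the column, a rejected suspect whose chart establishes non-amyloid HF joins the controls. Every such patient among the 422 is captured, while the controls are a separately chosen set of similar size. If eligible HF patients far outnumber the control charts, unweighted pooling gives rejected suspects much more weight than they have among people without the disease. Section 9.5 defines specificity for an individual without the disease, so the pooled figure would estimate something else. Rejected suspects may also be harder for the model, because something in their records already raised suspicion of the disease it looks for.

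A chart that supports neither diagnosis falls in neither column. Both metrics then describe only patients whose charts were clear.

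Specificity is one of two hypotheses to be tested. Its denominator should be fixed before the chart labels are known.

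**Working it through.** **Inputs from the plan.** One-sided α 0.05 (z = 1.645); power 0.90; specificity null 0.72, alternative 0.82, margin 0.10; cut point 0.7761; 422 potential cases.

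**Assumptions not in the plan.** 422 confirmed controls with specificity 0.82; m rejected suspects whose charts show non-amyloid HF; specificity s among them.

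**Step 1: the plan's own figures.** N = (z₀.₉₅ + z₀.₉₀)² p(1 − p)/M², with (1.6449 + 1.2816)² = 8.564.
- Sensitivity: 8.564 × 0.90 × 0.10/0.01 = 77.1, so 78, as stated.
- Specificity: 8.564 × 0.82 × 0.18/0.01 = 126.4, so 127, against 128 stated.
- Specificity cut point: 0.82 − 0.10 × 1.2816/2.9265 = 0.7762, against 0.7761 stated.

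The plan's figures reproduce to within rounding.

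**Step 2: unweighted pooling.** Estimate p = (422 × 0.82 + m × s)/(422 + m), with 422 × 0.82 = 346.04. Lower bound = p − 1.645 √[p(1 − p)/(422 + m)].

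| Rejects m (share of 422) | s | Estimate | Lower bound | Bound ≥ 0.72 | Estimate ≥ 0.7761 | Bound ≥ 0.7761 |
|---|---|---|---|---|---|---|
| left out | – | 0.820 | 0.789 | yes | yes | yes |
| 42 (10%) | 0.70 | 0.809 | 0.779 | yes | yes | yes |
| 42 (10%) | 0.60 | 0.800 | 0.770 | yes | yes | no |
| 106 (25%) | 0.60 | 0.7758 | 0.746 | yes | no, just | no |
| 106 (25%) | 0.40 | 0.736 | 0.704 | no | no | no |
| 211 (50%) | 0.60 | 0.747 | 0.718 | no | no | no |
| 211 (50%) | 0.40 | 0.680 | 0.650 | no | no | no |

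If s = 0.82 the estimate stays at 0.82 for any m. Three comparisons are shown because section 9.7.1 can be read as applying the cut point to the estimate or to the confidence bound.

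**Step 3: how low s must be.** The pooled estimate falls below 0.7761 when s < [0.7761(422 + m) − 346.04]/m.
- m = 42: (360.11 − 346.04)/42 = 0.335
- m = 106: (409.78 − 346.04)/106 = 0.601
- m = 211: (491.27 − 346.04)/211 = 0.688

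**Step 4: chance of passing.** The SE of the pooled estimate is √[422 × 0.82 × 0.18 + m s(1 − s)]/(422 + m), with a normal approximation. With rejects left out, the chance that the estimate reaches 0.7761 is 0.99. With 127 rejects (30%) at s = 0.60, the estimate is (346.04 + 76.2)/549 = 0.769, the SE is √(62.29 + 30.48)/549 = 0.0175, and the chance is 0.35. At s = 0.50 it is 0.04. The chance that the bound clears 0.72 goes from about 1.00 to 0.86 and 0.40 respectively.

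**Step 5: weighting by sampling fraction.** Take N eligible non-amyloid HF patients, of whom 211 are rejected suspects, all reviewed, so W = 211/N. The estimate is (1 − W) × 0.82 + W × s. Its SE is (1 − W) √(0.82 × 0.18/422), because rejects reviewed in full add no sampling error.
- N = 20,000, s = 0.40: W = 0.01055; estimate 0.8156; bound 0.8156 − 1.645 × 0.0185 = 0.785.
- N = 500,000, s = 0.60: W = 0.00042; estimate 0.8199; bound 0.789.

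Over these assumed pools the weighted estimate is 0.816 to 0.820, with a bound of 0.785 to 0.789.

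**The case against.** A reader might infer that section 9.6 drops rejected suspects while section 9.2.1 and Table 1 count them as controls, so that two stated rules collide. The text does not support this. Section 9.6 gives the label and stops. Section 9.2.1 and Table 1 place a rejected suspect among the controls only if the chart establishes non-amyloid HF. Most of the text (sections 9.1, 9.2.1, 9.3, 9.7.1 and 9.8) points to the chart label, and Appendix A may contain the disposition. What is shown is a rule not stated in the readable text.

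Charts that support neither diagnosis are not lost through a conflict either. Section 9.2.1 makes them ineligible, and section 9.8 provides for questions to be worked through until resolved. The remaining point is that their number and ML results would go unreported.

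The size of the effect rests on assumed reject numbers and specificities. At 10% rejected with specificity 0.70, the conclusion is the same on all three comparisons at the expected values. The plan also does not say that controls are a small fraction of eligible patients, so over-representation is conditional.

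Finally, weighting gives nearly the same answer as leaving rejects out, so it could be called unnecessary. It is a choice of target quantity, and it needs a random control draw. But it matches the plan's own definition of specificity, loses almost no precision, and does not remove the rejects from view.

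What survives is that the chart-label reading is the more natural one, and it is the one that leads to unweighted pooling.

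**Conclusion.** The concern holds in limited form. The readable plan does not fix the disposition of unconfirmed suspects, and following the chart label literally would pool them unweighted with the controls. Under the stated assumptions, 106 to 211 rejects at specificity 0.40 to 0.60 move the estimate from 0.82 to between 0.68 and 0.78. The lower bound moves from 0.789 to between 0.65 and 0.75. Those bounds straddle 0.72, and the estimates lie below 0.7761, one of them only just.

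It would be wrong to conclude that the specificity test will fail or that the plan contradicts itself. The effect needs many rejects with clearly lower specificity, and the documents give neither figure. The over-representation also requires eligible HF patients to far outnumber the control charts.

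**What to change.** Amend sections 9.6 and 9.7.1, and align Appendix A with them:

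1. Assign Table 1 columns by chart label alone, for suspects and controls alike, with a third outcome for indeterminate or other.
2. Draw controls at random from eligible HF patients with notes outside the 422, and record the sampling fraction.
3. Prespecify primary specificity as the estimate from the random controls, with rejected suspects entering only at their sampling weight. Report specificity among rejected suspects separately, and the unweighted pooled estimate as a sensitivity analysis.
4. Report indeterminate charts by ML result, with best-case and worst-case bounds for both sensitivity and specificity.

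The cost is protocol wording, a random draw and a few extra estimates, since all suspect charts are already to be reviewed. The downside is that specificity among rejected suspects may look less favourable. This is a cheap improvement that should be made before the chart labels are known.

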9.7. Data Analysis

9.7.1. Statistical Methods

The ML model will identify patients with HF as suspected ATTRwt-CM and the remainder patients as not suspected for ATTRwt-CM/non-amyloid HF. The patients with HF will be entered in the ML algorithm along with their diagnosis codes listed in all their records. The model will classify patients based on the presence and absence of cardiomyopathy features and categorized as suspected (at-risk) or not suspected with ATTRwt-CM. The model performance metrics (sensitivity and specificity) will be calculated by cross-tabulating between diagnosis based on ML algorithm and diagnosis based on chart ascertainment.

The analyses for noninferiority of sensitivity and specificity are straightforward. The calculations for these measures are shown below.

PFIZER CONFIDENTIAL

CT24-WI-GL02-RF02 4.0 Non-Interventional Study Protocol Template For Secondary Data Collection Study

01-Jun-2022

Page 19 of 25

Table 1. Sensitivity and Specificity

ML classification	Cohort (Ascertained by Charts)		TP+FP
	ATTRwt-CM	Non-amyloid HF	
+	True Positive (TP)	False Positive (FP)	TP+FP
-	False Negative (FN)	True Negative (TN)	TN+FN
	TP+FN	TN+FP	

Sensitivity = TP / (TP + FN)

Specificity = TN / (TN + FP)

We would then calculate the one-sided 95% confidence interval (CI) for sensitivity, assuming 90% power:

$$95\% \text{ CI} = \text{sensitivity} - 1.645(\text{SE}_{\text{sensitivity}})$$

where $\text{SE}_{\text{sensitivity}} = \text{square root} [\text{sensitivity} - (1-\text{sensitivity})]/n_{\text{sensitivity}}$

The 95% CI for sensitivity must equal or exceed a cut point (CP) value between 0.80 and 0.90 where:

$$\text{CP} = 0.90 - \text{NIM Z1-} \beta / (\text{Z1-}\alpha + \text{Z1-}\beta)$$

When $\alpha = 0.05$ and power = 0.90 we reject inferiority for all values $\geq \text{CP} = 0.8561$.

Similarly, for specificity, we reject inferiority for all values $\geq \text{CP} = 0.7761$.

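### The one-sided 95% Wald lower bound covers less than 95% at the plan's expected values for every n from 78 to 422; use an exact bound against the null values and restate the power at 78 cases and 128 controls

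*Combined protocol and SAP*

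**What the plan says.** Section 9.7.1 (Statistical Methods) introduces the interval with "We would then calculate the one-sided 95% confidence interval (CI) for sensitivity, assuming 90% power". The lower limit is the estimated sensitivity minus 1.645 times its standard error, and the standard error is computed from the estimate. The printed formula has a minus sign between the estimate and its complement where a product is expected.

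The decision rule follows: "The 95% CI for sensitivity must equal or exceed a cut point (CP) value between 0.80 and 0.90 where" CP = 0.90 - NIM × Z(1-β) / (Z(1-α) + Z(1-β)). With α = 0.05 "and power = 0.90 we reject inferiority for all values" at or above 0.8561. Specificity gets one sentence, "Similarly, for specificity, we reject inferiority for all values" at or above 0.7761.

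Section 9.5 (Study size) sets null values of 0.80 and 0.72, alternatives of 0.90 and 0.82, and a margin of 0.10 for both. It states: "For 90% power, the formula results in 78 individuals for sensitivity and 128 individuals for specificity". It also says that all 422 potential case charts and a similar number of control charts will be reviewed, and that before note review "one is unable to determine the total number of clinically diagnosed ATTRwt-CM patients".

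No section names an exact or score interval.

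**The concern.** For proportions of 0.8 to 0.9, a standard error computed from the estimate shrinks when the estimate happens to be high. The lower limit then sits too high in exactly the samples where it should be cautious. A nominal 95% lower limit of this form is therefore expected to cover less than 95%, whatever threshold it is later compared with.

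Two things are at stake. The lower limits are results in their own right, and they would overstate how well the algorithm's performance has been pinned down. The interval method also interacts with the decision rule. Comparing the bound with CP hides the under-coverage at the price of power, while comparing it with the null values exposes it as excess type I error. Separately, the phrase about assuming 90% power has no role in a confidence interval, because coverage does not depend on planned power.

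**Working it through.** **Inputs.** From section 9.5: nulls 0.80 and 0.72, alternatives 0.90 and 0.82, margin 0.10, sizes 78 and 128, ceiling of 422 potential case records. From section 9.7.1: multiplier 1.645, CP 0.8561 and 0.7761. Assumptions: the standard error is read as sqrt[s(1-s)/n], and n from 78 to 422 is taken as the plausible range for each group.

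**The plan's own figures.** N = (1.645 + 1.2816)² p(1-p) / 0.10².
- Sensitivity: 8.565 × 0.09 / 0.01 = 77.1, so 78, as stated.
- Specificity: 8.565 × 0.1476 / 0.01 = 126.4, so 127 against the stated 128.
- CP = 0.90 - 0.10 × 1.2816 / 2.9266 = 0.8562 (stated 0.8561).

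The formula uses the variance at the alternative only.

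**Coverage by hand at the planned sizes.** Coverage = P(lower limit ≤ true p), summed over the binomial distribution.
- n = 78, p = 0.90: the Wald limit is 0.890 at 73/78 and 0.908 at 74/78. It misses when X ≥ 74, which has probability 9.9%, so coverage is 90.1%. The exact limit first exceeds 0.90 at 75/78 (0.904), so coverage is 95.9%.
- n = 128, p = 0.82: the Wald limit is 0.818 at 111/128 and 0.827 at 112/128. P(X ≥ 112) = 6.2%, so coverage is 93.8%. The exact limit gives 96.4%.

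**Coverage over all 345 values of n from 78 to 422.**

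| True value | Wald range | Wald mean | n reaching 95% (Wald) | Clopper-Pearson minimum |
|---|---|---|---|---|
| 0.90 | 87.1% (n = 86) to 94.4% (n = 375) | 92.6% | 0 of 345 | 95.0% |
| 0.82 | 90.2% (n = 83) to 94.7% (n = 368) | 93.5% | 0 of 345 | 95.0% |

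At n = 422, Wald coverage is still 92.5% and 94.5%.

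**Effect on a reported limit (Wald, then exact).** 70/78: 0.841, 0.823. 90/100: 0.851, 0.836. 105/128: 0.764, 0.755. 380/422: 0.877, 0.873.

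**Effect on the decision.** Type I error is taken at 0.80 and 0.72, power at 0.90 and 0.82.

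| Rule | 78 cases: needed, type I, power | 128 controls: needed, type I, power |
|---|---|---|
| Wald ≥ CP (as written) | 71, 0.7%, 47.5% | 107, 0.16%, 37.0% |
| Wald against null | 68, 6.9%, 84.6% | 100, 7.2%, 89.3% |
| Exact against null | 69, 3.6%, 74.9% | 101, 4.7%, 84.8% |
| Exact ≥ CP | 73, 0.08%, 19.6% | 108, 0.07%, 28.5% |

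Over n = 78 to 422, Wald type I error against the null exceeds 5% at every n for sensitivity (mean 6.3%, maximum 9.2%). For specificity it exceeds 5% at all but one n (mean 5.9%, maximum 7.9%). Under the written rule it never exceeds 0.7%.

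With the exact limit against the null, 90% power is first reached at 112 cases and 152 controls. It holds at every n from 124 and 164 respectively up to 422.

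**The case against.** The strongest reply has four parts.

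- **Reading of the formula.** The coverage figures depend on correcting the printed standard error. Taken literally, s - (1-s) = 2s - 1, and sqrt[(2s-1)/n] gives coverage near 100%. If the square root covers only the numerator, coverage is about 54% to 76%. This stands as a condition on the numbers. Neither literal reading gives a 95% limit, so the formula has to be rewritten anyway.
- **Decision risk is conditional.** Under the written rule type I error is at most 0.7%, and the larger problem is the comparison with CP. That is correct. The 6.9% and 7.2% arise only if the comparison moves to the null while Wald is kept. The text can also be read as comparing the point estimate with CP, which would give type I error of 12.0% at 78 and 7.2% at 128. That ambiguity is another reason to rewrite the rule.
- **Power.** Much of the shortfall at 78 and 128 comes from the sample size formula, since Wald against the null also misses 90% there. The study will review all 422 potential case charts, and 124 confirmed cases would be about 29% of them (124/422). At 200 cases exact power is 99.1%. So the shortfall matters only near the stated minimums, but the plan says that the confirmed count is unknown.
- **Choice of method.** Clopper-Pearson is conservative: mean type I error against the null is 4.1% for sensitivity and 4.2% for specificity. Wilson is closer to nominal on average, at 4.7% and 4.8%, but reaches 5.8% and 6.0% at some n. Either is defensible if it is named in advance.

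Coverage also oscillates with n, so the means describe the defect better than any single value.

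**Conclusion.** The concern holds. With the standard error read as sqrt[s(1-s)/n], the nominal 95% lower limit averages 92.6% coverage at sensitivity 0.90 and 93.5% at specificity 0.82. It reaches 95% at no n from 78 to 422. The absolute effect on a reported limit is about 0.018 at 70/78 and under 0.004 at 380/422.

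The written rule does not inflate false claims; it loses power. The stated 90% power at 78 and 128 is not met under any version that compares a lower limit with either threshold. It is 47.5% and 37.0% as written, 84.6% and 89.3% for Wald against the null, and 74.9% and 84.8% for the exact limit against the null.

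The statement that coverage never reaches 95% applies at the expected values. At a true specificity equal to the null of 0.72, one n (412) just reaches 95.0%. The range of n is assumed, because 422 counts potential rather than confirmed cases. This should be corrected before analysis.

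**What to change.** In section 9.7.1, replace the Wald formula for both measures with wording such as: *The lower limit of the one-sided 95% Clopper-Pearson (exact binomial) confidence interval will be calculated. Inferiority is rejected for sensitivity if this limit is above 0.80 and for specificity if it is above 0.72. Wilson lower limits will be reported as supportive.* Delete the reference to 90% power from the interval definition, and remove CP from the decision rule. If the team prefers Wilson as primary, state that its type I error can reach 5.8% for sensitivity and 6.0% for specificity in this range of n.

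In section 9.5, replace the 90% power statement: with the exact limit against the null, power is 74.9% at 78 cases and 84.8% at 128 controls, and 90% holds from 124 cases and 164 controls up to 422.

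The interval and the threshold must change together. An exact limit with CP left in place gives only 19.6% and 28.5% power at the stated sizes, and Wald against the null exceeds 5% type I error.

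The cost is two short text changes and one line of Python. Compared with Wald against the null, the exact limit lowers power from 84.6% to 74.9% at 78 cases, from 92.7% to 87.6% at 100 cases, from 99.5% to 99.1% at 200 cases, and from 89.3% to 84.8% at 128 controls.

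### Section 9.7.1, as supplied, builds the standard error of sensitivity from a difference instead of the product p(1 − p); if the source page confirms the minus sign, the lower bound is too low and a pass can become a fail

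*Combined protocol and SAP*

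**What the plan says.** Section 9.7.1 of the combined protocol and SAP defines the analysis of sensitivity in three steps.

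- **SE:** "square root} [\text{sensitivity} - (1-\text{sensitivity})]/n_{\text{sensitivity".
- **One-sided 95% lower bound:** "CI} = \text{sensitivity} - 1.645(\text{SE}_{\text{sensitivity", that is, the estimate minus 1.645 SE.
- **Decision:** "The 95% CI for sensitivity must equal or exceed a cut point (CP) value between 0.80 and 0.90". At α = 0.05 and 90% power the cut point is given as 0.8561.

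For specificity, Section 9.7.1 says only "Similarly, for specificity, we reject inferiority for all values" at or above 0.7761. It writes out no SE.

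Section 9.5 states that sample size rests on a binomial approach and uses "Z_{1-\alpha} + Z_{1-\beta}) (p(1-p))^{0.5} / M" for the square root of N. It reports: "For 90% power, the formula results in 78 individuals for sensitivity and 128 individuals for specificity". The null hypothesis is "H0: Sensitivity ≤ 0.80", the alternative value is 0.90 and the margin is 0.10. The number of confirmed cases is not yet known; the plan is to maximise "potential cases by performing note review for all 422 charts".

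**The concern.** A binomial SE is √[p(1 − p)/n]. The expression in Section 9.7.1 has a minus where the product should be. Since p − (1 − p) = 2p − 1, it becomes √[(2p − 1)/n] with n under the root. That quantity is zero at p = 0.5, undefined below 0.5 and largest at p = 1, where the binomial SE is zero. It also conflicts with the variance term in Section 9.5.

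This SE feeds the lower bound on which the sensitivity decision rests. In the range of interest the bound would be too low, and an algorithm that meets the criterion could be declared to fail. No other section restates the SE.

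Two smaller gaps exist whatever the operator turns out to be. The bracket closes before the division by n, so it is not explicit that n lies under the root. The SE for specificity is left to inference.

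**Working it through.** **Inputs.** From Section 9.5: p = 0.90 under the alternative, 0.80 under the null, margin 0.10, stated N of 78, and 422 candidate charts. From Section 9.7.1: multiplier 1.645, cut point 0.8561, and 90% power (z = 1.282). The confirmed-case count is unknown. I use 78 (the planned minimum), 422 (every candidate chart confirmed) and 200 (an assumption).

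**1. Which variance term did the plan use?** N = (1.645 + 1.282)² × variance / 0.10², and 2.927² = 8.567.
- Product, 0.90 × 0.10 = 0.09: 8.567 × 0.09 / 0.01 = 77.1, rounded up to 78. This is the stated figure.
- Difference, 2 × 0.90 − 1 = 0.80: 8.567 × 0.80 / 0.01 = 685.4, rounded up to 686.

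Section 9.5 was therefore computed with the product.

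**2. Size of the SE error.** The ratio is √[(2p − 1) / (p(1 − p))].
- p = 0.85: √(0.70 / 0.1275) = 2.34
- p = 0.90: √(0.80 / 0.09) = 2.98
- p = 0.95: √(0.90 / 0.0475) = 4.35

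**3. Lower bound at an observed 0.90** (0.90 − 1.645 SE).

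| n | Product form | As printed |
|---|---|---|
| 78 | 0.844 | 0.733 |
| 200 | 0.865 | 0.796 |
| 422 | 0.876 | 0.828 |

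**4. Cases needed for an observed 0.90 to pass.**
- Against 0.8561: product 1.645² × 0.09 / 0.0439² = 126.4, so 127; printed 1.645² × 0.80 / 0.0439² = 1,123.3, so 1,124, which exceeds the 422 charts.
- Against 0.80: product 1.645² × 0.09 / 0.01 = 24.4, so 25; printed 1.645² × 0.80 / 0.01 = 216.5, so 217.

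**5. Which results change, and how often.** For every possible count of correctly flagged cases, I applied both SEs and noted those that pass with the product and fail as printed. The probability is the exact binomial sum over those counts at a true sensitivity of 0.90.

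| Bound compared with | n | Counts that change from pass to fail | Probability |
|---|---|---|---|
| 0.8561 | 78 | 71 to 78 | 0.475 |
| 0.8561 | 200 | 179 to 193 | 0.648 |
| 0.8561 | 422 | 373 to 392 | 0.864 |
| 0.80 | 78 | 68 to 76 | 0.844 |
| 0.80 | 200 | 169 to 180 | 0.529 |
| 0.80 | 422 | 351 to 366 | 0.018 |

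At n = 78 even 78/78 gives a printed bound of 1 − 1.645 × √(1/78) = 0.814, below 0.8561. No count at these sizes changes from fail to pass.

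**6. Where the effect is small or absent.** At n = 78 an observed 0.90 misses 0.8561 under either SE (0.844 and 0.733), so that result does not change. At n = 422 and a true sensitivity of 0.95, the probability of a changed result is 0.035 against 0.8561 and below 0.0001 against 0.80.

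**7. Specificity, if the same form were carried over.** At 0.82 the ratio is √(0.64 / 0.1476) = 2.08. With 422 controls the bound is 0.789 (product) or 0.756 (printed), against a cut point of 0.7761.

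**The case against.** The strongest objection is that the defect may not exist. It rests on one operator in machine-read text, and the notation of the nearby cut-point formula is visibly damaged. A dot or asterisk could have been read as a minus. This stands as uncertainty: nothing supplied settles it either way, so the point is conditional on the source page.

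Second, the intended form can be recovered from Section 9.5, and Section 9.8 provides for quality control of the programming, so a statistician would probably code it correctly. That lowers the chance of harm. But Section 9.7.1 defines the analysis, and a check of code against it as supplied would endorse the wrong SE or query the right one.

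Third, the figures against 0.8561 depend on comparing a confidence bound with the cut point, which is itself questionable. At n = 78 and a true 0.90, that rule passes with probability only 0.475 even with the correct SE, although 90% power is stated. So the 0.475 in the table is the rule's whole pass probability. If the point estimate were compared with the cut point instead, the SE would not enter the decision and only the reported bound would be wrong. This limits the weight of those figures. It does not remove the problem, because results also change against 0.80.

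Fourth, with n under the root the error is conservative: it produces no false claim of adequate sensitivity. That is correct. The cost is a false failure.

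Finally, n outside the root would make the SE too small (√0.80 / 78 = 0.0115 at n = 78). That reading is less natural and I do not rely on it.

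**Conclusion.** The concern holds as a conditional finding. As supplied, the SE in Section 9.7.1 is not a binomial SE and contradicts Section 9.5, whose 78 is reproduced by the product and not by the difference.

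If the minus is on the source page and is coded as printed, the SE is 2.98 times too large at 0.90. The harm against the null value of 0.80 is large with few cases (0.844 at n = 78) and nearly gone if all 422 charts are confirmed (0.018). Against 0.8561 it is substantial at all three sizes when true sensitivity is 0.90.

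These figures assume n under the root, a decision based on the lower bound, and the case counts named above. Confidence is medium because the operator cannot be checked here. The point should be fixed: it is essential if the page confirms the minus, and otherwise a minor clarification of where n sits and of the SE for specificity.

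**What to change.** Check the operator and the position of n on the source page. Then write both formulas out in Section 9.7.1:

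- SE of sensitivity = √[sensitivity × (1 − sensitivity) / number of confirmed cases]
- SE of specificity = √[specificity × (1 − specificity) / number of confirmed controls]

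with n explicitly under the root in each. The cost is one page check, one corrected line and one added line. Data collection does not change. This correction does not resolve the separate question of whether a confidence bound should be compared with the cut point at all.
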